### **Physical Therapy**

In part 1 the physical therapy only arm will only have to complete 2 in-person visits, baseline and the 3 month follow up, but they will receive two calls a week for the first three weeks to ensure consistency with the other treatment arms, and the virtual 6 week follow-up. The number of visits they will have to complete in part 2 will depend on which treatment arm the subject selects, but they will be required to come in at least once to complete the 6 month follow-up. The study will start when they enroll in the study and start the [name] protocol.

### **Shockwave**

The shockwave group will have 3 in-person visits and 3 virtual visits in part 1, and then at least one visit in Part 2 for the 6 month follow up. The number of visits required in part 2 will depend on what treatment the subject chooses at the 3 month check in.

### **Shockwave + Photobiomodulation therapy**

The PBMT and SWT treatment arm requires 6 in person visits in part 1 (3 for PBMT alone and 3 for PBMT & SWT), 1 virtual visit (6 week follow up) and at least 1 visit in part 2. The number of visits in part 2 will depend on which treatment the subject chooses at T8 (see table 1).

### **Study Visits for all treatment arms:**

An overview of the questionnaires and measurements that will be taken at various time points, regardless of treatment arm, are described in table 2.

Table 2: Overview of questionnaires and measurements required regardless of treatment arm

Visit	Questionnaires							Measurements	
	VISA-A	ProMIS-29	UWRI	Patient goals	Treatment preference	Patient satisfaction	Return to sports worksheet collection	Ultrasound	Heel raise & hopping test
Baseline	x	x	x	x	x			x	x
3-week follow-up	x	x	x				x		
6-week follow up	x	x	x				x		
3-month follow-up	x	x	x	x	x	x	x	x	x
6-month follow up	x	x	x	x	x	x	x	x	x

## **VI. BIOSTATISTICAL ANALYSIS**

### **a. Specific data variables being collected**

#### *Questionnaires:*

- Symptoms severity specific to Achilles will be **VISA-A**

- The VISA-A is currently the only valid and reliable measure to assess function and pain in AT (validity,  $P < 0.01$ ; test-re-test reliability,  $r = 0.98$ ) (2\*)
- ProMIS-29 will be used to capture other aspects of non-disease specific measures of health-related domains (physical, mental and social health).
- The University of Wisconsin Running Injury and Recovery Index (**UWRI**) will measure aspects unique to the running population.
- Visual analog scale of pain
- To quantify patient choice and motivation for treatment, an unvalidated survey will be obtained to determine patient goals of enrollment in study and reason for selecting a different intervention.
- Patient satisfaction with treatment
- **Participant demographics**
  - **Age at enrollment**
  - **Gender**
  - **Fitzpatrick skin type**
  - **Self-identified race and/or ethnicity**
  - **Marital status**
  - **Military status**
  - **Exclusion Criteria**
  - **BMI calculated from height and weight**
  - **Achilles tendon surgical history**
- **Expected AE interview forms**
  - **Achilles specific (one for each limb at week 1 check in, week 2 check in, 3 week follow-up, 6 week follow-up, 3 month follow-up, and 6 month follow-up)**

*Ultrasound:* Ultrasound measures will be assessed at baseline, 3 months and 6 months. Measures of interest include cross-sectional area, degree of thickening within the tendon at site of maximal circumference and maximal pain, and presence and number of neovessels on color flow doppler.

*Function:* Quantitative function in heel raises to fatigue will be measured at baseline, 3 months and 6 months on both affected and unaffected limb. We will also ask the participants to complete 20 hops and rate their pain using a visual analog scale (0 to 10).

*Return to running:* We will be asking participants to record their return to running, following Drs. Silbernagel & Crossley protocol. In order to log this, they will track the date, exercise and pain level using the University of Delaware training diary.

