## III. SUBJECT SELECTION

### a. Inclusion/Exclusion Criteria

#### Inclusion Criteria

Patients will be eligible if they meet the following criteria:

- Patients aged between 18-65 years old with a diagnosis of mid-portion Achilles tendinopathy (including both unilateral and bilateral)
- Running is the pre-injury primary form of physical activity and pre-injury would complete on average 10 miles per week or more of running
- VISA-A <80 at baseline to be eligible

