#### Exclusion Criteria

Exclusion criteria includes:

- Less than 3 months of symptoms
- Primary insertional Achilles tendinopathy
- Diagnosis of rheumatological disease/connective tissue condition, symptomatic arthritis of foot and ankle, a primary running related injury outside Achilles tendinopathy, other contraindications to PBMT or SWT
- Have received SWT within the past 3 months to their Achilles
- Prior injection within 3 months
- Currently enrolled in PT for more than 4 weeks for their condition
- Women who are pregnant or **those who are planning to become pregnant**. This is due to the fact that pregnancy will reduce participants activity after the treatment and the safety concerns related to shockwave treatment.
- Patients with neuropathy affecting sensation to pain
- Patients with a known underlying cardiac disease that could be affected by shockwave therapy
- Patients with known history of Achilles tendon rupture
- Patient currently taking oral steroids or fluoroquinolone antibiotics

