**b. Visit Details**

After consent has been obtained, patients will be randomly allocated to one of the three treatment arms. The expectations for the visits for the different study arms are outlined below:

Table 1: Outlined visits from three different study arms

	Physical Therapy only	Shockwave	PBMT & Shockwave
T0: Baseline	Subject screening & enrollment*		
Part 1	Subject to be randomly assigned a treatment arm		

T1: week 1 visit 1	VISA-A, ProMIS-29, UWRI, patient goals Ultrasound, heel raises & hopping test	Treatment 1 VISA-A, ProMIS-29, UWRI, patient goals Ultrasound, heel raises & hopping test	PBMT & SW treatment VISA-A, ProMIS-29, UWRI, patient goals Ultrasound, heel raises & hopping test
T2: week 1 visit 2	telephone check-in	telephone check-in	PBMT treatment only
T3: week 2 visit 1	telephone check-in	Treatment 2	PBMT & SW treatment
T4: week 2 visit 2	telephone check-in	Telephone check-in	PBMT treatment only
T5: week 3 visit 1	telephone check-in	Treatment 3	PBMT & SW treatment
T6: week 3 visit 2	telephone check-in VISA-A, ProMIS-29, UWRI	telephone check-in VISA-A, ProMIS-29, UWRI	PBMT treatment only VISA-A, ProMIS-29, UWRI
T7: 6 week follow up	telephone check-in VISA-A, ProMIS-29 & UWRI	telephone check-in VISA-A, ProMIS029 & UWRI	telephone check-in VISA-A, ProMIS-29 & UWRI
T8: 3 month follow up	VISA-A, ProMIS-29, UWRI, patient goals, patient satisfaction, new treatment selection Ultrasound, heel raise & hopping test	VISA-A, ProMIS-29, UWRI, patient goals, patient satisfaction, new treatment selection Ultrasound, heel raise & hopping test	VISA-A, ProMIS-29, UWRI, patient goals, patient satisfaction, new treatment selection Ultrasound, heel raise & hopping test
Part 2	Participants to choose treatment and follow visit schedule as listed above		
T9: 6 month follow up	Patient satisfaction, ultrasound, heel raises & hopping test	Patient satisfaction, ultrasound, heel raises & hopping test	Patient satisfaction, ultrasound, heel raises & hopping test

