## **VII. RISKS AND DISCOMFORTS**

### **Physical Therapy**

There are no expected risks or discomforts associated with the physical therapy, however physical therapy involves exercises designed to address causes of movement impairment, similar response to exercising muscles such as soreness and pain may be experienced. This is minimized by supervision by trained physical therapy using best practices to guide treatment.

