### **Shockwave**

The OrthoPlus Ultra 100 is a Class I FDA approved device with minimal risk. It is a low energy device and no severe events have been reported.

Reported discomforts of shockwave include bruising, swelling and rarely, tissue damage. Pain response is expected due to device treatment over sites of injury and use of process of clinical focusing; we will monitor each patient and adjust treatment settings to ensure pain is tolerable during the treatment.

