### **Adverse Event Causality Assessments**

Adverse events will be assigned a relationship (causality) to the treatments. The PI will be responsible for determining the relationship between the treatment and the AE. The type of event will help assess the likelihood that an AE is related to the treatment. Relationship of AEs to study products will be classified as follows:

- **Not Related:** No relationship exists between the AE and the treatment. The event is attributed to a pre-existing medical condition or an intercurrent event unrelated to the study device and procedures.
- **Possibly Related:** Follows the treatment, but may have been developed as a result of an underlying clinical condition or treatments/interventions unrelated to the study.
- **Probably Related:** Follows the treatment, but is unlikely to have developed as a result of the subject’s underlying clinical condition or other treatment or other interventions.

- **Definitely Related:** Follows the treatment and the physical evidence shows a convincing relationship to the treatment.
- **Unknown:** Follows the treatment, but unable to determine the relationship to the treatment.

Serious injury is defined to be an injury or illness that results in permanent impairment of a body function or permanent damage to a body structure, **or** necessitates medical or surgical intervention to preclude permanent impairment of a body function or permanent damage to a body structure that occurs during the course of the trial beginning after informed consent has been executed and extending until 30 days after the final study visit.

Partners IRB must be notified within 5 working days/ 7 business days of SAE discovery.

The Investigator is responsible for maintaining documentation in the study file that indicates the IRB has been properly notified.

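### In Part 1 the per-limb Achilles adverse-event form has no pre-treatment completion, so items that overlap the disease cannot be reliably classed as new or worsened within a participant

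*Combined protocol and SAP*

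**What the plan says.** - **Form schedule.** Section VI.a lists an Achilles-specific expected-AE interview form, "one for each limb at week 1 check in, week 2 check in, 3 week follow-up, 6 week follow-up, 3 month follow-up", plus 6 months. Baseline is not in the list.
- **Visit schedule.** In Table 1 (section V.b) both device arms have their first session at T1. The next row, "T2: week 1 visit 2", is the first to contain a check-in (by telephone, in the physical-therapy-only and shockwave arms). In the combined arm that row is a PBMT session. Neither Table 1 nor Table 2, captioned "Overview of questionnaires and measurements required regardless of treatment arm", shows the form at any visit.
- **Entry criteria (section III.a).** Inclusion requires "VISA-A <80 at baseline to be eligible". The first exclusion is "Less than 3 months of symptoms".
- **Expected effects (section VII).** For shockwave: "Reported discomforts of shockwave include bruising, swelling and rarely, tissue damage", and a pain response is also expected. For physical therapy, which all arms receive: "similar response to exercising muscles such as soreness and pain may be experienced".
- **Causality (section IX.b).** The PI assigns causality. The Not Related category includes this wording: "The event is attributed to a pre-existing medical condition or an intercurrent event unrelated to the study device and procedures". A Possibly Related category covers events that follow treatment but may stem from an underlying condition.
- **Safety review (section VI.c).** An interim review for safety and tolerance takes place after 30 participants are enrolled.

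**The concern.** Every participant has a symptomatic tendon before the first session. If the form records that Achilles pain is present at week 1, nothing on a matching earlier form shows whether it was there before, and whether it was milder. Such an entry can be counted as an event when it was carried over, or attributed to the existing condition when it was in fact a worsening. The plan has no rule for choosing between these, and the person who judges causality also delivers all the shockwave treatment, unblinded.

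At stake is how interpretable the early tolerance data are. The week 1 and week 2 forms fall inside the three-week device course, and the review at 30 participants would see about 10 per arm (30/3). Item status before treatment cannot be recovered once treatment has started.

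**Working it through.** The plan gives no AE rate, alpha or power, so there is no figure of its own to reproduce. The check has two parts.

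**1. Which per-limb information exists, and when**

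| Source | Before or at first session | Weeks 1–2 after first session | Next scheduled |
|---|---|---|---|
| Achilles AE form (VI.a) | none | week 1 and week 2 check-ins | 3 weeks |
| VISA-A, each tendon (V.a, Table 2) | baseline | none | 3 weeks |
| Heel raise and hop test with pain scale (VI.a, Table 2) | baseline | none | 3 months |
| Ultrasound (VI.a, Table 2) | baseline | none | 3 months |

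The pain visual analog scale listed among the questionnaires has no column in Table 2. The running diary records pain but is not described as per limb. General AE documentation at every visit (IX.a) records events, not status at entry. Table 1 places the baseline measures at T1 without saying whether they precede the T1 treatment. At weeks 1 and 2, then, the form is the only scheduled per-limb record, and it has no earlier entry to compare with.

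**2. Effect on a comparison of item presence between arms**

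Inputs: 20 per arm (IV.a, V.a). Everything else is assumed: two-sided 5% Fisher test, new-event risks p₁ (device) and p₂ (physical therapy only), and the same share b in each arm already positive and counted.

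Observed risk = b + (1−b)p, so observed difference = (1−b)(p₁−p₂).

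With p₁=50% and p₂=10%, power by exact enumeration:

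| b | Device | PT only | Difference | Power |
|---|---|---|---|---|
| 0% | 50% | 10% | 40 points | 74% |
| 30% | 65% | 37% | 28 points | 29% |
| 50% | 75% | 55% | 20 points | 18% |
| 70% | 85% | 73% | 12 points | 9% |

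A second model assumes that the control risk is b, and that the device adds the item in a share q of those otherwise negative. The device risk is then b + (1−b)q. With q=30%:

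| b | Device | PT only | Difference | Power |
|---|---|---|---|---|
| 5% | 33.5% | 5% | 28.5 points | 55% |
| 25% | 47.5% | 25% | 22.5 points | 22% |
| 50% | 65% | 50% | 15 points | 9% |
| 75% | 82.5% | 75% | 7.5 points | 5% |

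Both models show the same direction. Equal background does not create a false difference between randomised arms; it only shrinks a true one. A T1 form would not make the study well powered for safety either: at 30% against 10% with b=0, power is 24%.

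**The case against.** A reader might infer that device effects cannot be separated from the disease at all, or that tendon worsening would be hidden. The documents do not support either reading.

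- The randomised physical-therapy-only arm completes the same form and shows the background at group level.
- VISA-A, the primary outcome, is taken for each tendon at baseline, 3 weeks, 6 weeks and 3 months. Baseline ultrasound records cross-sectional area and thickening. A lasting deterioration would show there, whatever causality label an event receives.
- Not Related is a label, not a deletion. Events after consent are documented regardless, and Possibly Related is available for this overlap.
- The AE rule covers events occurring after consent, so counting a symptom that was already there would go against it.
- The background section attributes pain and limited movement to the disease. It says nothing about bruising, for which b may be close to zero. Soreness is described as a response to exercise, which every arm performs.
- The form's items are not shown. If it asks only about new or worsened symptoms, dilution would be small.
- Section VI.c does not name AEs as an outcome or tie the interim review to this form, and the study has no power calculation.
- The 3-month form falls at T8, where Part 2 treatment is chosen, so it may serve as a pre-treatment record for the cross-over.

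All of this stands and limits the point. It does not supply an item-level, per-limb reference for weeks 1 and 2. Group-level background does not settle an individual causality judgement, and the after-consent rule does not say how worsening of an existing symptom is recorded.

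**Conclusion.** The point holds as a data-collection gap in Part 1. No pre-treatment completion of the form is scheduled, no scoring rule covers symptoms present at entry, and items overlapping the disease cannot be reliably classed as new or worsened within a participant, most clearly at weeks 1 and 2. This reading takes the week 1 check-in to be T2 or later, as Table 1 implies.

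Any comparison of item presence between arms would be diluted by (1−b). The value of b is unknown and differs by item: plausibly substantial for pain, uncertain for swelling, perhaps negligible for bruising. The power figures only illustrate this under assumed rates, for a test that the plan does not specifically assign to AEs. They should not be read as the failure of a planned analysis. Severity is minor to moderate.

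**What to change.** 1. Complete the same form for each limb at T1, before the first treatment, in all three arms.
2. Add the form to Tables 1 and 2, and tie the week 1 and week 2 check-ins to named visits in every arm, including the combined arm, where T2 and T4 are treatment visits.
3. In the interim review and the safety tables, report by randomised arm up to T8 the items that are new or worse than the T1 entry for that limb, alongside all recorded events.
4. Leave the causality categories as they are, but have the T1 entry available when causality is judged. Barring Not Related for any item worse than at T1 would go too far, because natural or loading-related flares also occur without a device.

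The cost is one short extra form per limb at a visit already held in person, two table entries and a sentence in the analysis section. No visit, staff or treatment rule changes.

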**V. STUDY PROCEDURE**

**a. Overall Research Design and Methods**

This study has been split into two parts. **Part 1 is the initial randomized control trial, and Part 2 is when the participants can select the treatment they want to receive if they are not satisfied with their initial treatment.** In Part 1 patients will not be blinded to the treatment arm that they receive due to the obvious differences in the treatments.

Participants will also be asked to log their return to running at home using the University of Delaware Return to Sport protocol.

*Part 1*

Study participants will be randomly assigned to one of three treatment groups, using a block randomization generator **that is implemented into REDCap**. There will be 20 patients per treatment group, no power calculation as this is a feasibility study. The three treatment arms are: physical therapy only, SWT and physical therapy, and a combination of SWT, PBMT and physical therapy. All runners, regardless of treatment group, will be asked to enroll in physical therapy at a location that is convenient to them (and accepts their insurance if applicable) and complete a standard physical therapy program addressing individual strength deficits in both proximal (spine and hip girdle) along with distal (thigh, leg and foot/ankle) muscle groups. To standardize loading program, we will provide all runners with an at-home exercise program designed by [name] for progressive Achilles tendon loading. This will be

completed alongside the physical therapy they are receiving. Activities including running will be allowed as tolerated following published guidelines by [name].

In subjects who have bilateral AT, the leg with the most severe symptoms (determined by the VISA-A) will be chosen as the primary data for the study, however both legs will be treated consistent with the treatment group the subject was randomized into. Outcomes will be obtained for each Achilles tendon, regardless of treatment, using VISA-A at each data collection point. Participants will also be asked to complete a weekly log of running and completing PT exercises.

## Part 2

At the 3-month follow-up, participants who are not satisfied with their outcome will be given the option to choose one of the remaining treatment arms. Regardless of what treatment a patient chooses, if any, there will be one final visit conducted at 6 months for final data collection.

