**Shockwave (SWT) Arm:**

The shockwave arm will receive shockwave treatment in addition to the physical therapy program from [name]. They will receive one treatment a week and one telephone check-in a week for three weeks. [name], the PI, will perform the SWT on all study participants, using the OrthoPlus Ultra 100/radial D-Actor. This Extracorporeal Pressure Activation Treatment (EPAT) device will be used at a radial shockwave of 3000 counts treatment settings of 15 Hz minimum 2 bars with a focus applicator head at mid-portion of Achilles using clinical focusing technique, and 3000 counts at 15 Hz minimum 2.5 bars using broad oscillator to myotendinous region and over symptomatic areas of gastrocnemius and soleus. Maximal settings will be 4 bars and initial treatment will start at 500 strikes at 1.5 bars for each treatment head to allow participant to be comfortable as we start shockwave sessions. The research coordinator will conduct the telephone calls to check-in on physical therapy exercise compliance and response to each treatment.

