### **b. Study Endpoints**

Objective Endpoints

- Ultrasound endpoints
- Calf raises

Subjective Endpoints

- Questionnaires

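### No assessor masking is described for the ultrasound endpoints in a trial with unblinded participants; coded reading of stored images is a cheap safeguard

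*Combined protocol and SAP*

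**What the plan says.** - **Blinding.** Section V.a addresses participants only: "In Part 1 patients will not be blinded to the treatment arm that they receive due to the obvious differences in the treatments". No section mentions masking of assessors.
- **Label.** Section VI.b puts "Ultrasound endpoints" and calf raises under "Objective Endpoints"; questionnaires are listed as subjective.
- **Ultrasound.** Section VI.a states that "Ultrasound measures will be assessed at baseline, 3 months and 6 months". The measures are cross-sectional area, thickening at the widest and most painful sites, and "presence and number of neovessels on color flow doppler". No operator, reader, image storage or coding is mentioned.
- **Heel raises.** "Quantitative function in heel raises to fatigue will be measured at baseline, 3 months and 6 months on both affected and unaffected limb". No tester is named.
- **Who knows the arm.** Under the Shockwave Arm, the principal investigator "will perform the SWT on all study participants". The combined-arm text has photobiomodulation given by that investigator or by trained staff. The research coordinator's calls ask about response to treatment.
- **Timing.** In Table 1, T0 contains screening and enrolment, allocation follows, and the first ultrasound is at T1. In both device arms T1 is also the first treatment visit.
- **Use.** Section VI.c makes ultrasound and functional tests secondary to VISA-A and plans between-arm tests on them. Section II hypothesises improved tendon structure from baseline in every arm.

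**The concern.** An ultrasound measurement is objective only in so far as the person making it cannot be influenced by what they expect to see. Placing a calliper, choosing the level of greatest thickening and counting small vessels on Doppler all leave room for judgement. The roles that the protocol describes as having contact with participants during treatment can all learn the arm, and the plan does not keep any of them away from the images.

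Two comparisons are exposed. Knowledge of the arm can shift readings differently between arms and so bias the Section VI.c comparisons. Knowledge of the visit can shift follow-up readings relative to baseline and so bias the within-arm structural improvement hypothesised in Section II. Because Table 1 places the first scan after allocation, the baseline value is not protected either, and a change score could be affected at both ends.

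The questionnaires come from participants who know their treatment, and nothing can be done about that here. Ultrasound differs: once an image is stored, it can be measured by someone who cannot tell which arm or visit it came from.

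**Working it through.** **1. The plan's own figure.** Three arms of 20 give 3 × 20 = 60, as stated in Section IV.a. Section V.a says there is no power calculation. No alpha, SD, effect size or measurement-error figure is given, so the 5% level below is also an assumption.

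**2. What the documents settle.** Sections V.a, V.b, VI.a, VI.b and VI.c, with Tables 1 and 2, give the timing, content and analysis of the ultrasound measures. None gives an operator, a reader, a masking rule or a storage rule. The ultrasound and function paragraphs read as complete, with no removed text, so the silence is not a product of redaction. The supportable statement is that masking is not described.

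**3. Illustration of what unmasked reading could do.** Assume a continuous measure, no true difference, n = 20 per arm, and a differential reading shift of b SD between a device arm and physical therapy alone.

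- Standard error of the difference = √(2/20) = 0.316 SD.
- Two-sample t-test: noncentrality = b × √(20/2) = b × 3.162, on 38 degrees of freedom.
- Three-arm ANOVA with both device arms shifted by b: noncentrality = 20 × (2/3)b² = 13.33b², on 2 and 57 degrees of freedom.

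| Assumed shift b (SD) | t noncentrality | t-test error rate | ANOVA error rate |
|---|---|---|---|
| 0 | 0 | 5.0% | 5.0% |
| 0.2 | 0.632 | 9.5% | 9.0% |
| 0.3 | 0.949 | 15.2% | 14.5% |
| 0.5 | 1.581 | 33.8% | 33.7% |

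A normal approximation gives 9.7% at 0.2 SD and 15.8% at 0.3 SD, so the choice of test hardly matters. The covariate-adjusted regression also planned in Section VI.c was not modelled.

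**4. How much coded reading could recover.** Coding acts on the reading step only. Let f be the share of the bias that arises at reading and r the fraction of that share removed. The residual shift is b(1 − f·r). With b = 0.3 and r = 0.9, both assumed:

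| Share at reading f | Residual shift (SD) | t-test error rate |
|---|---|---|
| 1 | 0.3 × 0.10 = 0.030 | 5.1% |
| 0.5 | 0.3 × 0.55 = 0.165 | 8.0% |
| 0.25 | 0.3 × 0.775 = 0.2325 | 11.1% |

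Against 15.2% without coding, the gain runs from nearly complete to modest, depending on a share that the documents do not give.

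**5. Heel raises.** No image is read, so coding changes nothing. The count runs to fatigue and depends on the effort of a participant who knows the treatment.

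**The case against.** The strongest reply is that this is silence, not a stated flaw. The protocol never says that the reader knows the arm; the sentence on ultrasound is a schedule, and the sentence on the principal investigator concerns delivery of shockwave, not reading of scans. The endpoints are secondary, the trial is a feasibility pilot, and any size attached to the bias only restates the size assumed. All of that is right, and it limits the claim. It does not remove the point: Section VI.c plans between-arm tests on these measures, and nothing in the plan prevents unmasked reading.

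A reader might infer more than the documents support:

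- **That assessors are unmasked.** They may or may not be; the documents do not say.
- **That coded reading would remove most of the bias.** No figure supports this. The most painful site presumably has to be located with the participant during scanning, and Doppler capture may also be settled then.
- **That ultrasound is the trial's only protection against expectation effects.** Section V.b also partly matches contact, by giving the physical-therapy-only arm two calls a week for the first three weeks.
- **That the bias must favour the sponsor's hypothesis.** Section II expects structural improvement in every arm; the device-arm advantage is stated for running function, with structural change only part of the rationale.
- **That current staff can do this at no cost.** No reader is named, and export and coding are extra work.
- **That a tester who did not treat the participant would mask the heel-raise test.** Staff can learn the arm without treating, and participant effort would remain unmasked.

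**Conclusion.** The point holds in a limited form. Assessor masking is not described for ultrasound endpoints that the plan calls objective, and the plan as written permits reading with arm and visit known, from the first scan onwards if Table 1 is followed. That can bias the planned between-arm comparisons.

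The size is unknown. The range of about 9.5% to 15% against a nominal 5% rests wholly on an assumed 0.2 to 0.3 SD differential shift, 20 analysable participants per arm, a continuous measure and one comparison. It shows sensitivity and is not an estimate.

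This is a worthwhile low-cost improvement to secondary endpoints of a pilot, not a threat to its main result. VISA-A is patient-reported and is neither harmed by the gap nor helped by the fix.

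**What to change.** In the ultrasound paragraph of Section VI.a:

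1. State who scans and who reads.
2. Acquire stills and Doppler clips under a fixed acquisition protocol, and store them under a code that carries neither arm nor visit.
3. Have whoever would otherwise read the images measure all baseline, 3-month and 6-month images in random order, in one batch after the last 6-month visit.
4. If 3-month results are needed earlier, read baseline and 3-month images as a first coded batch, and state that the 6-month images form a second batch whose visit is therefore identifiable.
5. Acknowledge that coding masks reading only, so bias at acquisition can remain.
6. Report heel raises as an unmasked, effort-dependent measure. If coded reading is not adopted, report the ultrasound measures as unmasked too.

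The cost is image export and coding, the batch reading itself, and later availability of the measurements. Visits, treatments and sample size do not change.
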